8.2. MONITORING FOR ADVERSE EVENTS

At each visit following study informed consent form signature, after the subject has had the opportunity to spontaneously mention any problem, the Investigator or appropriate designee should inquire about AEs by asking the standard questions:

- “Have you had any health problems since your last study visit?”
- “Have there been any changes in the medicines you take since your last study visit?”

AEs should be reported for any clinically relevant change in concomitant condition(s) that is the result of an untoward (unfavorable and unintended) change in a subject's medical health. Changes in any protocol-specific systemic parameter evaluated during the study are to be reviewed by the Investigator. Any untoward (unfavorable and unintended) change in a protocol-specific parameter or questionnaire response that is clinically relevant is to be reported as an AE. These clinically relevant changes will be reported regardless of causality.

8.3. RECORDING OF ADVERSE EVENTS

All AEs (serious and non-serious) which occur from signature of the informed consent through patient participation in the study (last planned visit or early withdrawal date) will be collected and recorded in the eCRF. It is important that the AE dedicated section of the eCRF includes the duration of the AE (onset/resolution dates), the relationship to the drug, the severity, the outcome, the action(s) taken and relevant concomitant treatments dispensed. When possible, signs and symptoms indicating a common underlying pathology should be documented as one comprehensive event.

All AEs should be followed-up to determine the outcome of the reaction. The Investigator should follow up the event until resolution or stabilization of the condition. It is the Investigator's responsibility to assure that the subjects experiencing an AE receive definite treatment for any AE, if required.

Medical conditions/diseases present before starting study treatment shall be documented in the medical history section of the eCRF; these conditions are considered AEs only if they increase either in frequency or severity once informed consent has been signed.

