2.4. PHARMACOKINETICS AND PRODUCT METABOLISM

The pharmacokinetics of DF2156Y was studied in rats and mice after single i.v. and oral administration and after multiple oral administrations in rats and dogs within the toxicity studies.

DF2156Y is almost completely absorbed after oral administration in rats with an absolute bioavailability higher than 90%. DF2156Y is slowly eliminated from plasma in all the three species tested ($t_{1/2}$ ranging from 25 hours to 30 hours). Gender differences in pharmacokinetic profile after oral administration (slightly lower exposure in females than in males) were observed in rats but not in dogs.

A metabolite of DF2156Y named DF2108Y (R enantiomer) was identified, using a non-chiral analytical method, in both rats and dogs. On the basis of the chiral analytical determination, the S enantiomer (DF2227Y) was noted in the plasma of both rats and dogs. The *in vivo* interconversion of DF2108Y into DF2227Y was about 90% in rats.

In male and female rats DF2227Y was the major and long-lasting circulating metabolite. After repeated daily oral administration of ladarixin, this metabolite showed an accumulation ratio ranging between 1.4 and 2.4. After the daily oral administration of ladarixin at 200 mg/kg for 6 weeks, the parent compound and the metabolites showed comparable exposure in Wistar and Sprague Dawley rats either at day 1 or after repeated administrations.

In humans, single oral doses of ladarixin (25 to 400 mg) provided quantifiable plasma concentration of DF2156Y within 1 hour, with peak concentration being reached between 1 and 3 hours. After single doses, DF 2156A was excreted mainly as unmodified in human urine. The presence of the two metabolites found in animal species (DF 2108Y and DF 2227Y) was confirmed in humans. Dose proportionality over the entire dose range investigated was observed as well as $t_{1/2}$ (11-19 h) remained constant across the range of doses evaluated. Renal clearance accounted for approximately 60-80% of the total clearance of ladarixin. The dose proportionality for the main PK parameters was also seen for the two metabolites (DF 2108Y and DF 2227Y).

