After multiple doses, DF 2156Y reached the steady state around Day 5 and 6 following 50, 100, 200, 300 and 400 mg b.i.d. Systemic exposure to ladarixin, DF 2108Y and DF 2227Y appeared to increase in a dose-proportional manner. The clearance and the volume of distribution of ladarixin appeared to be dose-independent on both Days 1 and 8 for all doses. Similarly, $t_{1/2}$ (ranging from 11 to 18 h) remained constant on Day 1 and on Day 8 across the range of doses evaluated.

Co-administration of ladarixin increased the exposure and urinary excretion of tolbutamide while decreasing the exposure and the urinary excretion of tolbutamide metabolites. Plasma tolbutamide AUC values increased by about 2-fold and the AUCs of the metabolites decreased by about 2-fold. Thus, ladarixin can be classified as a moderate inhibitor of CYP2C9.

In vitro ladarixin appears to be a strong inhibitor of the enzyme CYP2C9 in humans (83%) and a moderate inhibitor in rats (51%). No inhibition was observed in dogs. No inhibition was detected in any species with regard to CYP2D6. Also, no inhibition was shown for CYP 1A2, 2C19, and 2E1 with respect to humans and dogs, but a moderate inhibition was shown in rats (about 50%). As to CYP3A4, a slight inhibition was seen in all species which was higher than 20% only in rats (about 28%). In humans, co-administration of ladarixin (200 mg twice a day for 5 days) approximately doubled the exposure to tolbutamide (probe for CYP2C9 isoenzyme).

Preliminary *in-vitro* protein binding studies showed that ladarixin is highly bound to plasma proteins; binding varies according to ladarixin concentrations and appears to be saturable: mice 97.7%, rats 91.8-99.4%, dogs 80.4-99.5% and humans 93.0-99.9%. Repeated at 400 mg b.i.d. administrations in humans confirmed the very high binding to plasma proteins (>99.99%).

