5.2. DOSE, ROUTE AND SCHEDULE OF IMP ADMINISTRATION

Ladarixin will be administered orally at the dose of 400 mg b.i.d. for 7 cycles of 14 days with an interval of 14 days off, for a total duration of 26 weeks. The two daily doses will be administered at about a 12-hour interval (morning and evening; ideally between 6:30/11:30 and 18:30/23:30). At each administration, 2 capsules will be swallowed with a glass of water, at least 2 hours apart from breakfast or dinner. Placebo will be administered with the same treatment schedule.

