6.1.2. Visit schedule and events/procedures

All subjects will follow the study procedures outlined below (see also grid in [Section 2](#) above).

Every effort should be made to adhere to the visit schedule. Visits should be scheduled at the designated time-point. If unavoidable, an unscheduled visit may be performed, but the schedule for subsequent visits must be maintained so that the total duration of the study period per patient is as close as possible to 30 weeks. If a visit is scheduled at a time other than the protocol designated time, careful consideration must be given to the amount of study medication the subject has available.

Patients should be counseled to fast (no food or drink except water and non-study medications as prescribed) for at least 8 hours prior to all study visits where blood will be collected.

Each patient will be involved in the study for a screening visit, a randomization visit, the treatment period of 26 weeks (14 days on /14 days off) with 3 follow-up visits to the clinical research site scheduled up to week 28 after the 1st IMP dose.

Visit schedule and events/procedures are detailed in the sections below. Visits 2b and 3 are scheduled during the 14 days off treatment, while visit 4 is set in the 2 weeks after treatment completion (last IMP dose in cycle 7).

CCI

Visit 1: Screening: The study physician or designee will present to/discuss with the study subject the clinical trial and answer all questions. If the patient is able and willing to participate, after the informed consent has been obtained, study staff will:

- assess past medical history to confirm T1D (e.g. results of past auto-antibody testing),
- determine daily insulin requirement (U/kg/day - expressed as the average of the last 3 days) and its stability,
- measure body weight, height, waist and waist/hip circumference,
- calculate [REDACTED] BMI,
- record the use of concomitant medication,
- establishing the presence of IR as described (inclusion criteria, bullet 8)¹⁻³.

Screening evaluation also include blood sampling for the assessment of:

- HbA1c,
- fasting C-peptide,
- standard safety laboratory tests,

- pregnancy in subjects with reproductive potential; post-menopausal women, defined as no menses for 12 months without an alternative medical cause, will not undergo pregnancy testing.
- T1D auto-antibody (excluding IAA) should past data not be available.

Vital signs (blood pressure and heart rate) will be measured and an ECG performed.

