Visit 2b: (Week 4): An ECG will be performed and then the subject will undergo blood sampling for assessment of safety laboratory testing.

Visit 3: (Week 11/12): Patient Kits (cycle 1 to 3) and the Diary will be returned to and checked by the study staff to verify inventory and treatment compliance. Medication use will be also ascertained. Vital signs will be measured followed by an ECG, and then the subject will undergo blood sampling for assessment of HbA1c and safety laboratory testing and exploratory outcome measures CCI [REDACTED]; average (previous 3 days) daily insulin requirements (IU/kg/day) will be recorded, body weight, height, waist and waist/hip circumference will be measured and [REDACTED] CGM data will be downloaded for measurement of glycemic variability in the previous 7 days. After IMP discontinuation criteria have been checked, Patient Kits (cycle 4 to 7) will be dispensed and the subject will be discharged from this visit.

Visit 4; End of Study (Week 27/28): The study subject will come to the clinic for final assessment of vital signs, ECG, average (previous 3 days) daily insulin requirements (IU/kg/day), body weight, height, waist and waist/hip circumference and for [REDACTED]. Subjects will undergo blood sampling for assessment of HbA1c, safety laboratory testing, eGFR and exploratory outcome measures CCI [REDACTED] CGM data will be downloaded for measurement of glycemic variability in the previous 7 days.

At the end of the visit, upon the study physician's order, the subject will be formally discharged from the study.

REGULARLY-SCHEDULED PHONE CALLS: In-trial, the sub-investigator/study coordinator will proactively reach out to study subjects, at least every 30-45 days, for the entire study period from the time

of randomization visit onwards, to ensure compliance with treatment and importantly, ongoing identification of any AEs. It is the responsibility of the PI to adjust the frequency of such contacts, according to patient responsiveness and compliance with treatment.

Unscheduled visits

In addition to the scheduled visits, it is possible that subjects may need to complete an unscheduled visit if they experience an event that the PI or the Principal Physician believes to warrant follow-up. The unscheduled visit might include appropriate actions, such full physical examination and blood sample collection (less than 30 mL) that the PI or the Principal Physician feels is required, based upon the event.

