7.2. SAFETY ENDPOINTS

- Vital signs (blood pressure and heart rate) [Timeframe: screening, week 11/12 (visit 3), 27/28 (visit 4)]
- Laboratory tests [haematology (total WBC, neutrophils/lymphocytes/monocytes/basophils/eosinophils (% and absolute number), total RBC, MCV, hematocrit, platelet count) and clinical chemistry (sodium, potassium, serum creatinine, serum albumin, total bilirubin, ALT, AST)] [Timeframe: screening, week 11/12 (visit 3) and 27/28 (visit 4)]
- Incidence of Treatment Emergent Adverse Events (TEAEs), Adverse Drug Reaction (ADR) and Treatment Emergent Serious Adverse Events (TESAEs) [Timeframe: from the beginning of IMP administration up to the end of study participation].

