8.3.1. Follow-up of patients with AEs

The Investigator is responsible for adequate and safe medical care of subjects during the trial and for ensuring that appropriate medical care and relevant follow-up procedures are maintained after the trial. All AEs should be followed-up to determine outcome of the reaction. The Investigator should follow up the event until

resolution or stabilization of the condition. It is the Investigator's responsibility to assure that the subjects experiencing AEs receive definite treatment for any AE, if required.

If subject was hospitalized due to a SAE, a copy of the discharge summary is to be forwarded to the Sponsor as soon as it becomes available. In addition, a letter from the Investigator that summarizes the events related to the case, as well as results of any relevant laboratory tests and redacted section of medical records may be provided to the Sponsor, if relevant for the SAE. In case of death, a copy of the autopsy report, if performed, should also be provided.

The Investigator shall inform the Sponsor with an appropriate written communication, whenever he becomes aware of new available information regarding the SAE, once the condition is resolved or stabilized and when no more information about the event is expected. Follow-up SAE information should be processed as initial SAE notification (see Sections 8.4, 8.5).

For pharmacovigilance purposes, all SAEs should be followed-up in order to clarify as completely as possible their nature and/or causality and until all queries have been resolved. All SAEs will be followed up until the events resolve or the events or sequelae stabilize, or it is unlikely that any additional information can be obtained after demonstration of due diligence with follow-up efforts (i.e. subject or Investigator is unable to provide additional information, or the subject is lost to follow up), unless subject has withdrawn his/her consent.

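### Minor: adverse-event collection ends at visit 4, which may fall from day 183, a few hours to a few days after the last dose and while parent drug may still be present

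*Protocol*

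**What the plan says.** Section 8.3 collects all adverse events from consent; those occurring "through patient participation in the study (last planned visit or early withdrawal date) will be collected and recorded in the eCRF". Section 7.2 gives the timeframe for TEAEs, ADRs and TESAEs as "from the beginning of IMP administration up to the end of study participation", and the synopsis agrees.

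The last planned visit is visit 4, labelled week 27/28. Section 6.1.2 says "visit 4 is set in the 2 weeks after treatment completion (last IMP dose in cycle 7"). At the end of that visit "the subject will be formally discharged from the study". The regular calls in 6.1.2 cover the study period only, and no later contact is scheduled.

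On dosing, section 5.2 gives seven 14-day cycles separated by 14-day breaks, 26 weeks in total, with morning and evening doses "ideally between 6:30/11:30 and 18:30/23:30". On elimination, section 2.4 gives a human half-life after single doses of "11-19 h) remained constant across the range of doses evaluated", and after repeated doses one "ranging from 11 to 18 h) remained constant on Day 1 and on Day 8".

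For what follows visit 4, section 8.3.1 states "All AEs should be followed-up to determine outcome of the reaction", which concerns events that have already begun. Section 8.4.1 has the investigator report a later SAE on becoming aware of it, and notes that active monitoring is not usually needed once the trial is over.

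**The concern.** An event that starts while study drug is still in the body belongs in the TEAE and ADR incidences, and safety is a secondary objective. Here the collection period is tied to a visit, and the visit window opens the morning after the last dose. A patient seen on the first permitted day is discharged with a substantial share of the last-dose level still present, and nobody is due to ask about events after that.

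This is also the end of the longest exposure in the trial. Section 2.5.3 describes earlier repeated-cycle experience of three cycles; here there are seven. Section 8.1 treats all ADRs as unexpected, so non-serious events help to build the safety profile as well.

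**Working it through.** **Calendar.** Seven on-periods and six breaks give 7 × 14 + 6 × 14 = 182 days = 26.0 weeks, which reproduces the stated duration. Cycle 7 starts on day 1 + 6 × 28 = 169 and ends on day 182. Week 27/28 is days 183-196, or 14 days. As a cross-check, week 4 (days 22-28) and weeks 11/12 (days 71-84) fall in the breaks after cycles 1 and 3, as section 6.1.2 requires of visits 2b and 3.

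**Inputs.**
- Last dose: 18:30-23:30 on day 182 (5.2).
- Half-life t: 11, 18 and 19 h, the ends of the two ranges in 2.4.
- Visit time: 08:00-11:30. This is an assumption; fasting blood sampling makes a morning visit likely.
- Washout criterion: five half-lives. This is an assumption, since the protocol states none. It leaves 0.5^5 = 3.1%. Four and six are also tried.

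**When washout ends.** Time needed = k × t after the last dose.

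| k | t = 11 h | t = 18 h | t = 19 h |
|---|---|---|---|
| 4 | 44 h: day 184, 14:30-19:30 | 72 h: day 185, 18:30-23:30 | 76 h: day 185, 22:30 to day 186, 03:30 |
| 5 | 55 h: day 185, 01:30-06:30 | 90 h: day 186, 12:30-17:30 | 95 h: day 186, 17:30-22:30 |
| 6 | 66 h: day 185, 12:30-17:30 | 108 h: day 187, 06:30-11:30 | 114 h: day 187, 12:30-17:30 |

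With five half-lives, morning visits are too early on days 183-184 (t = 11 h; 2/14 = 14% of the window) or days 183-186 (t = 18 or 19 h; 4/14 = 29%). With four, the days are 183-184 (2/14 = 14%) or 183-185 (3/14 = 21%).

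**How much parent drug is left.** Hours since last dose on day d = 24 × (d − 183) + 8.5 to 17. Share of the last-dose level remaining = 0.5^(hours/t), assuming simple exponential decline.

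| Visit day | Hours | t = 11 h | t = 18 h | t = 19 h |
|---|---|---|---|---|
| 183 | 8.5-17 | 34.3-58.5% | 52.0-72.1% | 53.8-73.3% |
| 184 | 32.5-41 | 7.6-12.9% | 20.6-28.6% | 22.4-30.6% |
| 185 | 56.5-65 | 1.7-2.8% | 8.2-11.4% | 9.3-12.7% |
| 186 | 80.5-89 | 0.4-0.6% | 3.2-4.5% | 3.9-5.3% |
| 187 | 104.5-113 | 0.08-0.14% | 1.3-1.8% | 1.6-2.2% |

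**What the proposed limit achieves.** Five days after a day-182 dose is day 187. A morning contact that day comes 104.5-113 h after the dose, past the 95 h needed at t = 19 h. The added collection is at most 187 − 183 = 4 days.

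**The case against.** The protocol is consistent with itself: 7.2, 8.3 and the synopsis all stop at the end of participation, and no section promises a washout. The five-half-life rule comes from outside the document. Section 6.1.2 asks that a patient's total duration stay near 30 weeks, which with two weeks of screening points to about week 28. Events present at visit 4 are followed, later SAEs can still be reported, and section 10.3 tells patients that safety data might be collected after participation. Completers have six earlier 14-day breaks under observation, so an effect of stopping would have had six chances to appear. Finally, redacted text follows directly on the sentence that places visit 4, and a timing rule could sit there.

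Much of this stands, and it is why the point is minor. The redaction limits the claim to the legible text. The 30-week aim favours later visits but does not exclude day 183. The follow-up rules do not lead anyone to ask about a new non-serious event after visit 4, and section 10.3 schedules nothing. The earlier breaks are reassuring but follow shorter cumulative exposure. The choice of multiple moves the last affected day but does not remove the gap: with four half-lives, days 183-184 or 183-185 are still early.

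A reader might infer more: that the comparison between arms is biased, that SAEs go unreported, or that many patients are affected. The documents do not support this. The rule is the same in both arms, SAEs keep a passive route, and the distribution of visit 4 dates is not known. Nor can anything be said about the metabolites, whose human half-life is not given.

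**Conclusion.** The point holds as a minor, cheap improvement. The legible protocol allows active adverse-event collection to stop from day 183, when 34-73% of the last-dose parent level would remain at a morning visit. Under five half-lives the exposed visit days are 183-184 (11 h) or 183-186 (18-19 h), at most 4 of 14. At 18 h, a visit late on day 186 would already be clear.

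The possible loss is confined to new non-serious events starting in the few days after an early visit 4, together with active capture of new SAEs in those days. The result rests on the assumed washout multiple, a morning visit, and an evening dose on day 182 taken as scheduled. No efficacy analysis is touched.

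**What to change.** In 8.3, 7.2 and the synopsis, collect AEs and SAEs to visit 4 or to 5 days after the last IMP dose actually taken, whichever is later. If visit 4 falls earlier than that, make one closing safety call when the 5 days are up, under the existing call procedure of 6.1.2 and with the two standard questions of 8.2. Count that call as the patient's last contact for End of Study (6.4) and for database lock.

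Counting from the dose actually taken means that a patient who stopped IMP more than 5 days before visit 4 needs no call. The visit 4 window and its assessments stay as they are. Do not extend the whole prohibited-medication list of 5.5.2, because efficacy assessment is finished by then. At most, advise against starting narrow-index CYP2C9 drugs until the call, since section 2.4 classes ladarixin as a moderate CYP2C9 inhibitor.

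The cost is a short amendment and an occasional phone call by existing staff. Database lock could move by a few days at most, and only if the last patient attends early.

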8.3.1. Follow-up of patients with AEs

The Investigator is responsible for adequate and safe medical care of subjects during the trial and for ensuring that appropriate medical care and relevant follow-up procedures are maintained after the trial. All AEs should be followed-up to determine outcome of the reaction. The Investigator should follow up the event until

resolution or stabilization of the condition. It is the Investigator's responsibility to assure that the subjects experiencing AEs receive definite treatment for any AE, if required.

If subject was hospitalized due to a SAE, a copy of the discharge summary is to be forwarded to the Sponsor as soon as it becomes available. In addition, a letter from the Investigator that summarizes the events related to the case, as well as results of any relevant laboratory tests and redacted section of medical records may be provided to the Sponsor, if relevant for the SAE. In case of death, a copy of the autopsy report, if performed, should also be provided.

The Investigator shall inform the Sponsor with an appropriate written communication, whenever he becomes aware of new available information regarding the SAE, once the condition is resolved or stabilized and when no more information about the event is expected. Follow-up SAE information should be processed as initial SAE notification (see Sections 8.4, 8.5).

For pharmacovigilance purposes, all SAEs should be followed-up in order to clarify as completely as possible their nature and/or causality and until all queries have been resolved. All SAEs will be followed up until the events resolve or the events or sequelae stabilize, or it is unlikely that any additional information can be obtained after demonstration of due diligence with follow-up efforts (i.e. subject or Investigator is unable to provide additional information, or the subject is lost to follow up), unless subject has withdrawn his/her consent.

